4.3.6.4.3 Tumor Infiltrating Immune Cell (TIIC) Numbers and Profiles Pre-Treatment and On-Treatment

Preexisting tumor immune infiltration is associated with increased likelihood of tumor response to checkpoint inhibition.^{41,42} This association between tumor immune infiltration and increased response to immunotherapy may be due to preexisting tumor-specific T cell clones within the tumor which have been primed by tumor antigens but attenuated by checkpoint signaling, which are then activated upon checkpoint inhibition.

To explore the impact of tumor immune infiltration in biliary cancers treated with the combination of pembrolizumab plus induction GM-CSF, archival pre-treatment tumor core biopsy or resection samples (primary and/or non-nodal metastatic site depending on availability) will be obtained when available. Pending funding and adequate sample size, the samples may be examined in batch for immune cell infiltrates (TIIC) and T cell subset composition in batch at study completion in the laboratory of [name] at UCSF as has been previously described.^{33,39,43} The presence of TIIC and immune cell subset composition will be explored for association with clinical outcomes including PFS, ORR, DOR, OS, and CA 19-9- response.

If available from a standard of care tissue sampling event, , such as in cases for which an on-treatment or post-treatment tumor resection or biopsy is required for clinical care (e.g. palliative metastatectomy/debulking, biopsy of an equivocal lesion, or if fiducial placement is required for palliative radiotherapy), paired archival on-treatment or post-treatment tumor samples will also be analyzed in comparison to the baseline/pre-treatment specimen.

In the Expansion Cohort, paired biopsies will be obtained on pembrolizumab and on pembrolizumab plus GM-CSF to ascertain the relative impact of pembrolizumab alone compared to pre-treatment archival sample, then the impact of addition of GM-CSF to pembrolizumab compared to pre-treatment and compared to pembrolizumab monotherapy. It is expected that GM-CSF effect will be apparent after 2 weeks of exposure based upon tumor tissue analyses showing increased tumor T cell infiltration in prostate cancer patients treated with GM-CSF prior to radical prostatectomy.¹²

In Expansion Cohort biopsy samples, TIIC studies will be performed in batch at conclusion of study, pending additional grant funding. TIIC in tumor tissue will be compared descriptively to paired PBMC from the same patient (Section 4.3.5.3.2).³³ TIIC will be quantified and individual immune cell subsets profiled by IHC and other methods in paired FFPE biopsy specimens including but not limited to: cytotoxic CD8+, helper CD4+FOXP3-, and regulatory CD4+FOXP3+ T cells. The proportion of activated T cells (defined using markers such as PD1+ and Ki67+) will also be analyzed, as will myeloid-derived suppressor cells (using markers such as M2 CD68/Arg-1, M1 CD68/iNOS). Other techniques such as laser capture microdissection may be used if needed to isolate tumor from microenvironment, pending funding and depending on standard IHC results.

In Expansion Cohort biopsy samples, tumor infiltrating T cell TCR clonotypes, gene expression profiles, and/or other analytes may also be analyzed by next generation sequencing and other methods, pending funding and adequate sample availability. If performed, these analyses will be performed on pre-treatment archival tumor samples if adequate material is available as well as from fresh frozen or FFPE core biopsy samples 1) on pembrolizumab monotherapy and 2) in combination with GM-CSF.

4.3.6.4.4 Tumor Genotype and Association with Response Outcomes, PD-L1 status, T-cell Infiltration, and TCR Repertoire

Higher tumor mutation burden (TMB) and genomic instability are associated with increased likelihood of response to pembrolizumab in non-small cell lung cancers.^{19,20} It is thought that increased mutational burden overall, as well as certain specific mutations, may be immunogenic.

Multiple clinical trials are now available for genotype-defined populations in cholangiocarcinoma, including *FGFR2* fusions and *IDH1* or *IDH2* mutations.⁴⁴ It is expected that the majority of patients enrolled on this study will have had targeted tumor next generation tumor sequencing such as FoundationOne (<http://foundationone.com>) performed as standard of care prior to enrollment, based upon emerging evidence for targeted therapies in advanced biliary cancers.

For patients with available tumor sequencing results performed as part of clinical care, specific mutations, pathways, TMB, and presence of genomic instability-related mutations will be explored for association with clinical outcomes including PFS, RR, DOR, and OS. The tumor mutation profile and TMB will also be explored for association with PD-L1 status and presence of immune infiltrates, based upon emerging evidence that specific tumor mutations can impact T cell infiltration and activation.^{19,45}

5.0 METHODOLOGY

5.1 Entry Criteria

5.1.1 Diagnosis/Condition for Entry into the Trial for All Cohorts

1. Histologically- or cytologically-diagnosed advanced or locally-advanced biliary cancer not eligible for resection or other curative therapies, including:
 - a. Intrahepatic (peripheral) cholangiocarcinoma;

- b. Extrahepatic cholangiocarcinoma including hilar/perihilar (Klatskin), middle, and distal locations;
- c. Gallbladder carcinoma (GBC);
- d. Mixed/combined hepatocellular-cholangiocarcinoma;
- e. Ampullary carcinoma and pancreas ductal adenocarcinoma are NOT eligible.

2. Clinical and/or radiographic progression on ≥ 1 prior systemic treatment regimen with cytotoxic chemotherapy, targeted therapy, and/or investigational therapy for advanced biliary cancer. Cumulative toxicity or intolerance (such as progressive cytopenias, neuropathy, or asthenia on a 1st line regimen of gemcitabine plus cisplatin) requiring treatment discontinuation of ≥ 1 prior systemic treatment regimen is also sufficient for eligibility. There is no maximum eligible prior number of lines of therapy provided all eligibility criteria are met. Adjuvant chemotherapy including gemcitabine and/or fluoropyrimidine after prior surgical resection of CCA or GBC will be considered as 1 line of prior therapy if relapse/recurrence with incurable disease occurred within ≤ 6 months of last dose.

5.1.2 Subject Inclusion Criteria for All Cohorts

In order to be eligible for participation in this trial, the subject must:

1. Be willing and able to provide written informed consent for the trial.
2. Be ≥ 18 years of age on day of signing informed consent.
3. Have a performance status of 0 or 1 on the ECOG Performance Scale.
4. Demonstrate adequate organ function as defined in Table 1; all screening labs should be performed within 28 days of treatment initiation.

Table 1 Adequate Organ Function Laboratory Values

System	Laboratory Value
Hematological	
Absolute neutrophil count (ANC)	$\geq 1,000 / \text{mcL}$
Platelets	$\geq 60,000 / \text{mcL}$ ($\geq 75,000 / \text{mcL}$ in Expansion Cohort, see below)
Hemoglobin	$>9 \text{ g/dL}$ or $\geq 5.6 \text{ mmol/L}$ without transfusion or EPO dependency (within 7 days of assessment)
Renal	
Serum creatinine OR Measured or calculated ^a creatinine clearance (GFR can also be used in place of creatinine or CrCl)	$\leq 1.5 \times$ upper limit of normal (ULN) OR $\geq 60 \text{ mL/min}$ for subject with creatinine levels $> 1.5 \times$ institutional ULN
Hepatic	
Serum total bilirubin	$\leq 1.5 \times$ ULN OR Direct bilirubin \leq ULN for subjects with total bilirubin levels > 1.5 ULN

AST (SGOT) and ALT (SGPT)	≤ 5 X ULN
Albumin	≥ 2.5 g/dL
Coagulation	
International Normalized Ratio (INR) or Prothrombin Time (PT)	≤ 1.5 X ULN unless subject is receiving anticoagulant therapy as long as PT or PTT is within therapeutic range of intended use of anticoagulants
Activated Partial Thromboplastin Time (aPTT)	≤ 1.5 X ULN unless subject is receiving anticoagulant therapy as long as PT or PTT is within therapeutic range of intended use of anticoagulants

^aCreatinine clearance should be calculated per institutional standard.

5. Patients with known hepatitis B or C virus (HBV or HCV) infection are eligible provided liver function parameters meet laboratory eligibility criteria in Table 1.
 - a. Patients with active HBV infection must have monitoring of viral load and demonstrate adequate treatment with appropriate antiviral therapy according to institutional practice.
 - b. Patients with active HCV infection must have monitoring of liver function tests and viral load if indicated according to institutional practice.
6. Female subject of childbearing potential should have a negative urine or serum pregnancy within 72 hours prior to receiving the first dose of study medication. If the urine test is positive or cannot be confirmed as negative, a serum pregnancy test will be required.
7. Female subjects of childbearing potential should be willing to use 2 methods of birth control or be surgically sterile, or abstain from heterosexual activity for the course of the study through 120 days after the last dose of study medication (Reference Section 5.7.2). Subjects of childbearing potential are those who have not been surgically sterilized or have not been free from menses for > 1 year.
8. Male subjects should agree to use an adequate method of contraception starting with the first dose of study therapy through 120 days after the last dose of study therapy.

5.1.3 Additional Expansion Cohort Subject Inclusion Criteria

1. Presence of ≥ 1 target lesion measurable by RECIST 1.1¹ not planned for biopsy.
2. Presence of ≥ 1 tumor lesion accessible for paired on-treatment minimally-invasive percutaneous biopsies (CT, ultrasound or punch), as assessed by investigator and/or radiologist; this lesion may be included as a target or non-target lesion for RECIST 1.1.
3. Platelet count $\geq 75,000/\text{mcL}$
4. No contraindication to tumor biopsy at time of study enrollment.
5. Consent for on-treatment paired biopsies.

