4.3.5.1 Rationale for Expansion Cohort Schedule and Biopsies

An important exploratory objective of the Expansion Cohort is to obtain paired biopsy samples from patients while on treatment with pembrolizumab monotherapy and in combination with GM-CSF, in addition to archival pre-treatment samples. Correlative analyses of tumor and TIIC PD-L1 expression, TIIC profiles, and PBMC profiles will explore for changes associated with

pembrolizumab alone and with addition of GM-CSF to better understand the differential contributions of each study drug to the observed clinical and radiographic responses in this study.

To enable comparisons of pembrolizumab monotherapy and in combination with GM-CSF, the schedule for the Expansion Cohort will be the same as the Safety Cohort, starting with 1 cycle of pembrolizumab monotherapy before adding induction GM-CSF during Cycles 2 and 3. The observed safety and efficacy of the Safety Cohort and Efficacy Cohort are similar, though limited by small sample sizes, supporting the choice of the Safety Cohort schedule for the Expansion Cohort. Biopsies will be planned during Week 3 of pembrolizumab monotherapy and Week 9 after addition of GM-CSF and after first restaging imaging has been obtained. PMBC profiles will be compared between the Safety and Expansion Cohorts (expected n=23) and the Efficacy Cohort (n=18), enabling further characterization of the impact of GM-CSF on immune cell profiles in a larger group of subjects.

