^a Core needle biopsies (CNB) will be obtained in Expansion Cohort subjects with lesions safely amenable to percutaneous biopsy (by assessment of proceduralist, Section 5.1.3) during Cycle 1 on approximately C1D15 (±3 days) and during Cycle 3 approximately C3D15 ±3 days, preferably after completion of restaging imaging for 8 week time point. See Appendix 11.6.3 for processing instructions.

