7.1.4.3 Expansion Cohort Research Biopsies

Expansion Cohort enrollment requires radiographic assessment of measurable disease by RECIST 1.1 with ≥ 1 target lesion not planned for biopsy, as well as tumor accessible to minimally-invasive percutaneous biopsy (by CT, ultrasound, or punch) based upon assessment of qualified radiologist. More invasive methods of biopsy such as surgery, laparoscopy, or endoscopy are not allowed for purposes of research biopsy on this study due to patient risk. Consent for paired research biopsies during Cycle 1 and Cycle 3 is required for enrollment to Expansion Cohort. Two to 4 core needle biopsies (CNB), preferred 18-gauge and 1 cm depth (or equivalent) if safely accessible based upon evaluation by proceduralist, should be obtained at each time point (Section 6.4) with prioritization and handling instructions per Appendix 11.6.3. Biopsy samples will be analyzed for exploratory biomarker endpoints as described in 4.3.6.4

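### Section 5.1.3 lets the biopsied lesion be a RECIST target although an unbiopsied one is already mandatory, so an exploratory procedure can enter the primary ORR: a small effect that is cheap to remove

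*Combined protocol and SAP*

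**What the plan says.** Section 5.1.3 adds two lesion requirements for the Expansion Cohort. Criterion 1 asks for at least one measurable target lesion "not planned for biopsy". Criterion 2 asks for at least one lesion suitable for paired percutaneous biopsy (CT-guided, ultrasound-guided or punch) and adds that "this lesion may be included as a target or non-target lesion for RECIST 1.1".

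Section 7.1.4.3 sets the sampling at each time point: "Two to 4 core needle biopsies (CNB), preferred 18-gauge and 1 cm depth". The Section 6.4 footnote sets the timing: "during Cycle 1 on approximately C1D15 (±3 days) and during Cycle 3 approximately C3D15 ±3 days, preferably after completion of restaging imaging". On the second biopsy the places differ in strength. Section 4.3.5.1 plans it for "Week 9 after addition of GM-CSF and after first restaging imaging has been obtained", and the cell in the Section 6.4 flow chart also puts it after scans. The footnote makes that order a preference only.

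Scans are at screening and then every 8 weeks from C1D1, ±7 days for the first 6 months (Sections 6.4 and 7.1.2.6). The primary endpoint is ORR by locally assessed RECIST 1.1. It counts CR and PR, confirmed or not, at any time in the main study (Sections 4.3.6.1, 8.3.1 and 8.6.1). Section 4.3.5.1 describes the biopsies as serving an exploratory objective.

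Sections 7.1.2.6, 8.3.1, 8.5.2 and 8.6.1 contain no rule for measuring a target lesion after biopsy, no new baseline for it, and no sensitivity analysis that leaves it out.

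**The concern.** Criterion 1 keeps one target lesion untouched, and criterion 2 lets a sampled lesion back into the same sum of diameters. A change in that lesion caused by the needle or punch then counts as if the drugs had caused it. Bleeding or inflammation can enlarge the lesion. Sampling a small or superficial lesion can reduce it.

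The trial has one arm, so no control group carries the same error. The decision also turns on very few responders. Because an unconfirmed response at any single scan counts, a spurious PR would stay in the numerator. Spurious growth could hide a PR at one scan or be read as progression, which would also touch PFS6.

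**Working it through.** **1. Timing** (day 1 = C1D1, 21-day cycles, nominal schedule)

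- First biopsy, C1D15 ±3: days 12 to 18.
- Second biopsy, C3D15: 2 × 21 + 15 = day 57; ±3 gives days 54 to 60.
- Week-8 scan: 56 days after day 1 = day 57; ±7 gives days 50 to 64.

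The first biopsy always follows the pre-treatment baseline and precedes the week-8 scan, by 50 − 18 = 32 to 64 − 12 = 52 days. Under the footnote, the scan can follow the second biopsy by up to 64 − 54 = 10 days. Under Section 4.3.5.1 and the flow-chart cell it cannot. In either case both biopsies precede all later scans.

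**2. The plan's own power figures**

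Inputs from Sections 8.4.1 and 8.6.1: n = 37, H0 5%, H1 20%, stated power 88% (1-sided 5%) and 77% (2-sided 5%). The plan names Fisher's exact test; I used the one-sample exact binomial, P(X ≥ r), X ~ Bin(37, p).

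| Cut-off | P at p = 0.05 | P at p = 0.20 | Plan states |
|---|---|---|---|
| ≥5 of 37 | 3.6% | 88.8% | 88% |
| ≥6 of 37 | 1.0% | 77.8% | 77% |

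Both figures are reproduced. One patient is 1/37 = 2.7 points of ORR.

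**3. Exposure**

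The ceiling is 15/37 = 40.5%. It assumes that every Expansion patient is evaluable, is biopsied, and has the biopsied lesion chosen as a target. Appendix 11.6.3 expects at least 12 with paired biopsies (12/37 = 32.4%). The documents do not say how many biopsied lesions are targets.

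**4. Tissue lost to cores**

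Assumption: core bore 0.8 to 1.0 mm, lesion spherical, full collapse of the space left. Volume removed per biopsy = number of cores × π × bore²/4 × 10 mm.

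- Smallest: 2 × π × 0.8²/4 × 10 = 10 mm³. Largest: 4 × π × 1.0²/4 × 10 = 31 mm³.
- 15 mm lesion: volume π × 15³/6 = 1767 mm³. Loss 10/1767 = 0.6% to 31/1767 = 1.8%. Diameter falls by at most 15 × (1 − 0.982^(1/3)) ≈ 0.09 mm.
- 10 mm lesion: 2% to 6% of volume, 0.06 to 0.2 mm in diameter.

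For comparison, take a PR threshold of a 30% fall in the sum (an assumption here, because the documents cite RECIST 1.1 without restating it) and baseline targets of 15 + 25 = 40 mm. Moving a true −27% to −30% needs 0.03 × 40 = 1.2 mm, and moving −25% to −30% needs 0.05 × 40 = 2.0 mm. Core loss of about 0.09 mm falls far short. A change of 1 to 2 mm from bleeding, inflammation or a punch would be enough near the threshold. The documents give no punch size and no rate for such changes.

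**5. What misclassification would do, if it occurred**

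Let m be the chance that biopsy turns an Expansion non-responder into a responder. This is an assumed range, with no value in the documents. Under H0 each exposed patient then responds with probability 0.05 + 0.95m and the others with 0.05; the two binomial counts are added. Ranges are for 12 to 15 exposed patients.

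| m | Type I error, ≥5/37 | Type I error, ≥6/37 |
|---|---|---|
| 0 | 3.6% | 1.0% |
| 2% | 5.4–6.0% | 1.6–1.8% |
| 5% | 9.1–10.9% | 3.1–4.0% |
| 10% | 17.3–22.4% | 7.2–10.2% |

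In the other direction, let biopsy hide a true response with probability m, so that exposed patients respond with 0.20(1 − m). At m = 10%, power falls from 88.8% to 86.4–86.9% (≥5) or from 77.8% to 74.0–74.8% (≥6).

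**The case against.** The strongest reply is that the plan already dealt with this. Criteria 1 and 2 do not contradict each other: the authors foresaw biopsy interference and required an untouched target, which dilutes any effect in the sum. Cores of the stated size hardly change a diameter. Section 7.1.2.7 lists punch as one mode of core needle biopsy, and nothing describes removing most of a lesion. Temporary swelling at week 8 does not erase a later response, because ORR counts response at any time. For apparent progression within 6 months, Section 5.8 lets the Study Chair allow a clinically stable patient to continue to another scan, and Section 8.3.2 records no PFS event if that later imaging does not show progression. The second-biopsy problem comes down to one word in a footnote, and the 10-day gap needs both windows at opposite extremes.

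Most of this stands, and it limits the size. It does not remove the point. The untouched target dilutes the biopsied one but does not exclude it, the Section 5.8 provision is discretionary, and no measurement rule covers a biopsied target.

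A reader might infer that coring alone could shrink a lesion enough to turn SD into PR. Step 4 of the working does not support that. A reader might also infer that the primary ORR of patients already enrolled should be recomputed without the biopsied lesion. The documents give no basis for that, and in an open-label trial with local reads it would change how the primary endpoint is measured after responses are visible.

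**Conclusion.** The point holds as a minor weakness in the protection of the primary endpoint. Non-drug changes in a biopsied target can enter ORR in at most 15 of about 37 evaluable patients. The plausible routes are bleeding, inflammation, or sampling of a small or punch-accessible lesion. The expected effect is small and its direction is not fixed. It deserves attention because one reclassified patient is worth 2.7 points when the cut-off is 5 or 6 of 37, and because the exposure is avoidable.

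A reader might take the type I error table as a forecast. It is not: m is assumed, all error is pushed one way, and all 12 to 15 patients are taken as exposed. For tissue loss from cores, m would be near the low end of the range. The core-volume result rests on the assumed bore and a spherical lesion. The exposure figure is a ceiling.

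**What to change.** 1. **Future Expansion patients.** Amend Section 5.1.3 criterion 2 so that the biopsied lesion is recorded as non-target. Criterion 1 always supplies another target, so no eligible patient is lost, and n = 37, the cut-offs and the power stay as they are. The cost is fewer target lesions in some sums, occasionally only one. A biopsied non-target lesion can still bear on CR or progression calls, but no longer on the sum.
2. **Footnote in Section 6.4.** Delete the word *preferably*, so that the week-8 scan comes before the second biopsy as in Section 4.3.5.1 and the flow-chart cell. This is a wording change only.
3. **Patients already enrolled with a biopsied target.** Keep the primary ORR as measured. Record on the CRF which lesion was biopsied, and pre-specify an ORR sensitivity analysis using unbiopsied target lesions only. Criterion 1 makes this computable for every Expansion patient. The cost is one CRF field and one extra table.

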5.1.4 Subject Exclusion Criteria for All Cohorts

The subject must be excluded from participating in the trial if the subject:

- 1) Is currently participating and receiving study therapy or has participated and received study therapy in a study of an investigational agent, or used an investigational device within 4 weeks of the first dose of treatment.
- 2) Has a diagnosis of immunodeficiency or is receiving systemic steroid therapy for purposes of immunosuppression or any other form of immunosuppressive therapy within 7 days prior to the first dose of trial treatment.
- 3) Has a known history of active TB (Bacillus Tuberculosis).
- 4) Has a known history of Human Immunodeficiency Virus (HIV) (HIV 1/2 antibodies).
- 5) Has untreated active Hepatitis B (e.g., HBsAg reactive).
- 6) Has an active infection requiring systemic antibiotic therapy at time of enrollment.
 - a) Treatment with antibiotic prophylaxis for indwelling biliary stent(s) or peri-procedural antibiotics for uncomplicated biliary stent exchanges is allowed and not an exclusion.
- 7) Hypersensitivity to pembrolizumab or any of its excipients.
- 8) Has received treatment with an anti-cancer monoclonal antibody (mAb) within 4 weeks prior to study Day 1 or who has not recovered (i.e., \leq Grade 1 or at baseline) from adverse events due to agents administered more than 4 weeks earlier.
- 9) Has received treatment with chemotherapy, targeted small molecule therapy, or radiation therapy to non-liver sites within 2 weeks prior to study Day 1 or who has not recovered (i.e., \leq Grade 1 or at baseline) from adverse events due to a previously administered agent administered more than 2 weeks earlier.
 - a) Subjects with \leq Grade 2 neuropathy or alopecia are an exception to this criterion and may qualify for the study.
 - b) If subject received major surgery, they must have recovered adequately from the toxicity and/or complications from the intervention prior to starting therapy.
- 10) Has had prior chemoembolization, bland embolization, radioembolization, local ablative therapies, radiation to liver tumors, or major surgery such as liver resection within 4 weeks prior to study enrollment or who has not recovered (i.e., \leq Grade 1 or at baseline) from adverse events due to intervention more than 4 weeks earlier.
- 11) Has a known additional malignancy that is progressing or requires active treatment. Exceptions include basal cell carcinoma of the skin or squamous cell carcinoma of the skin that has undergone potentially curative therapy or in situ cervical cancer.

- 12) Has known active central nervous system (CNS) metastases and/or carcinomatous meningitis. Subjects with previously treated brain metastases may participate provided they are stable (without evidence of progression by imaging for at least four weeks prior to the first dose of trial treatment and any neurologic symptoms have returned to baseline), have no evidence of new or enlarging brain metastases, and are not using steroids for at least 7 days prior to trial treatment. This exception does not include carcinomatous meningitis which is excluded regardless of clinical stability.
- 13) Has active autoimmune disease that has required systemic treatment in the past 2 years (i.e. with use of disease modifying agents, corticosteroids or immunosuppressive drugs). Replacement therapy (e.g., thyroxine, insulin, or physiologic corticosteroid replacement therapy for adrenal or pituitary insufficiency, etc.) is not considered a form of systemic treatment.
- 14) Has known history of or any evidence of active, non-infectious pneumonitis.
- 15) Has had prior organ or stem cell transplantation.
- 16) Has a history or current evidence of any condition, therapy, or laboratory abnormality that might confound the results of the trial, interfere with the subject's participation for the full duration of the trial, or is not in the best interest of the subject to participate, in the opinion of the treating investigator.
- 17) Has known psychiatric or substance abuse disorders that would interfere with cooperation with the requirements of the trial.
- 18) Is pregnant or breastfeeding, or expecting to conceive or father children within the projected duration of the trial, starting with the pre-screening or screening visit through 120 days after the last dose of trial treatment.
- 19) Has received prior therapy with an anti-PD-1, anti-PD-L1, or anti-PD-L2 agent.
 - a) This criterion does not apply to eligibility for Second Course treatment.
- 20) Has received a live vaccine within 30 days of planned start of study therapy.
 - a) Seasonal influenza vaccines for injection are generally inactivated flu vaccines and are allowed; however intranasal influenza vaccines (e.g., Flu-Mist®) are live attenuated vaccines, and are not allowed.

